11.1.4.3 Evaluation of New Lesions

The finding of a new lesion should be unequivocal (i.e. not due to difference in scanning technique, imaging modality, or findings thought to represent something other than tumor (for example, some 'new' bone lesions may be simply healing or flare of pre-existing lesions). However, a lesion identified on a follow-up scan in an anatomical location that was not scanned at baseline is considered new and will indicate PD. If a new lesion is equivocal (because of small size etc.), follow-up evaluation will clarify if it truly represents new disease and if PD is confirmed, progression should be declared using the date of the initial scan on which the lesion was discovered.

11.1.4.4 **Evaluation of Best Overall Response**

The best overall response is the best response recorded from the start of the treatment until disease progression/recurrence (taking as reference for progressive disease the smallest measurements recorded since the treatment started). The patient's best response assignment will depend on the achievement of both measurement and confirmation criteria.

For Participants with Measurable Disease (i.e., Target Disease)

Target Lesions	Non-Target Lesions	New Lesions*	Overall Response	Best Overall Response when Confirmation is Required*
CR	CR	No	CR	>4 wks Confirmation**
CR	Non-CR/Non- PD	No	PR	
CR	Not evaluated	No	PR	→4 wks Confirmation**
PR	Non-CR/Non- PD/not evaluated	No	PR	
SD	Non-CR/Non- PD/not evaluated	No	SD	Documented at least once ≥4 wks from baseline**
PD	Any	Yes or No	PD	
Any	PD***	Yes or No	PD	no prior SD, PR or CR
Any	Any	Yes	PD	

^{*} See RECIST 1.1 manuscript for further details on what is evidence of a new lesion.

Note: Participants with a global deterioration of health status requiring discontinuation of treatment without objective evidence of disease progression at that time should be reported as "symptomatic deterioration." Every effort should be made to document the objective progression even after discontinuation of treatment.

For Participants with Non-Measurable Disease (i.e., Non-Target Disease)

|--|

^{**} Only for non-randomized trials with response as primary endpoint.

^{***} In exceptional circumstances, unequivocal progression in non-target lesions may be accepted as disease progression.

CR	No	CR
Non-CR/non-PD	No	Non-CR/non-PD*
Not all evaluated	No	not evaluated
Unequivocal PD	Yes or No	PD
Any	Yes	PD

^{* &#}x27;Non-CR/non-PD' is preferred over 'stable disease' for non-target disease since SD is increasingly used as an endpoint for assessment of efficacy in some trials so to assign this category when no lesions can be measured is not advised

11.1.5 **Duration of Response**

Duration of overall response: The duration of overall response is measured from the time measurement criteria are met for CR or PR (whichever is first recorded) until the first date that recurrent or progressive disease is objectively documented (taking as reference for progressive disease the smallest measurements recorded since the treatment started, or death due to any cause. Participants without events reported are censored at the last disease evaluation).

Duration of overall complete response: The duration of overall CR is measured from the time measurement criteria are first met for CR until the first date that progressive disease is objectively documented, or death due to any cause. Participants without events reported are censored at the last disease evaluation.

Duration of stable disease: Stable disease is measured from the start of the treatment until the criteria for progression are met, taking as reference the smallest measurements recorded since the treatment started, including the baseline measurements.

11.1.6 **Progression-Free Survival**

Overall Survival: Overall Survival (OS) is defined as the time from randomization (or registration) to death due to any cause, or censored at date last known alive.

Progression-Free Survival: Progression-Free Survival (PFS) is defined as the time from randomization (or registration) to the earlier of progression or death due to any cause. Participants alive without disease progression are censored at date of last disease evaluation.

Time to Progression: Time to Progression (TTP) is defined as the time from randomization (or registration) to progression, or censored at date of last disease evaluation for those without progression reported.

12. DATA REPORTING / REGULATORY REQUIREMENTS

12.1 Data Reporting

The ODQ will collect, manage, and perform quality checks on the data for this study.

12.2 Data Safety Monitoring

The DF/HCC Data and Safety Monitoring Committee (DSMC) will review and monitor toxicity and accrual data from this study. The committee is composed of clinical specialists with experience in oncology and who have no direct relationship with the study. Information that raises any questions about participant safety will be addressed with the Overall PI and study team.

The DSMC will review each protocol up to four times a year or more often if required to review toxicity and accrual data. Information to be provided to the committee may include: up-to-date participant accrual; current dose level information; DLT information; all grade 2 or higher unexpected adverse events that have been reported; summary of all deaths occurring with 30 days of intervention for Phase I or II protocols; for gene therapy protocols, summary of all deaths while being treated and during active follow-up; any response information; audit results, and a summary provided by the study team. Other information (e.g. scans, laboratory values) will be provided upon request.

12.3 Multicenter Guidelines

This protocol will adhere to the policies and requirements of the DF/HCC Multi-Center Data and Safety Monitoring Plan. The specific responsibilities of the Overall PI, Coordinating Center, and Participating Institutions and the procedures for auditing are presented in Appendix B.

- The Overall PI/Coordinating Center is responsible for distributing all IND Action Letters or Safety Reports to all participating institutions for submission to their individual IRBs for action as required.
- Mechanisms will be in place to ensure quality assurance, protocol compliance, and adverse event reporting at each site.
- Except in very unusual circumstances, each participating institution will order the study agent(s) directly from supplier. A participating site may order the agent(s) only after the initial IRB approval for the site has been forwarded to the Coordinating Center.

13. STATISTICAL CONSIDERATIONS

13.1 Study Design/Endpoints

Original Primary Endpoint (when trial opened).

The primary endpoint of this trial was to evaluate the proportion progression-free at 10 months in patients with MTC. A Simon two-stage design was used to minimize the number of patients exposed to this regimen and the specific sample size and operating characteristics were chosen to be able to rule out a proportion progression-free at 10 months of 20%. The rate chosen for this null hypothesis was based on the following considerations:

Elisei et al (10) trial showed a proportion progression-free at 10 months of approximately 60% vs 20% on the cabozantinib vs. placebo arms respectively. The population in that trial was a mix of patients receiving treatment in the 1st and second line setting. This current trial is for a similar patient population, but is for patients who have received any prior number of lines of therapy, including at least on targeted therapy. Regorafenib may also have a similar or a more favorable toxicity profile.

Original Statistical Design for patients with MTC (when the trial opened).:

A two-stage design was used where if ≥ 10 patients were alive and disease was progression-free at 10 months among 31 evaluable (eligible and began protocol treatment) patients (assuming that ≥ 4 patients among 18 evaluable patients accrued in the first stage were alive and disease is progression-free at 10 months), further testing of this regimen was to be considered. The probability of concluding the regimen was effective was 85% if the true proportion progression-free was 40%. The probability of concluding the regimen as effective was 7% if the true proportion progression-free was 20%. Allowing 2 patients to not begin protocol treatment or be classified as ineligible, a total of 33 patients were to be entered.

Revised Statistical Design for patients with MTC (2018).:

Changes to the statistical design were needed to be in line with the rarity of the MTC as well as the corresponding observed slow accrual.

A two-stage Simon optimal design was used where if ≥ 7 patients were alive and disease was progression-free at 10 months among 21 evaluable (eligible and began protocol treatment) patients (assuming that ≥ 2 patients among 8 evaluable patients accrued in the first stage were alive and disease progression-free at 10 months), further testing of this regimen was to be considered. The probability of concluding the regimen was effective was 81% if the true proportion progression-free was 42%. The probability of concluding the regimen as effective was 10% if the true proportion progression-free was 20%. Allowing 2 patients to not begin protocol treatment or to be classified as ineligible, a total of 23 patients with MTC were to be entered.

Rationale for Patient Population and Design Changes (2019).

A total of 8 patients with MTC have been enrolled. Due to the changing treatment landscape/other treatment options for patients with MTC, the trial will no longer enroll patients with MTC. Patients with DTC will now be enrolled in order to obtain preliminary information on efficacy using regorafenib in this patient population.

Revised Endpoint and Statistical Design for patients with DTC

With only 2 treatment options currently FDA approved for RAIR DTC and their corresponding response rates, the study chair felt that an overall response rate >25% by using regorafenib would be worth further study. The below design and specific operating characteristics were chosen to rule out a best overall response rate of 25% by studying approximately n=22 patients with DTC. Therefore ,keeping within the original overall accrual goal from when the trial opened (approximately 31 (n=8 MTC plus n=22 DTC)) and that only large improvements in response will be able to be detected statistically.

A two-stage Simon optimal design will be used to stop the trial early if there is minimal activity in this patient population. In the first stage, accrual will continue until 9 evaluable patients (eligible and begin protocol treatment) with DTC are entered. If there are \leq 2 patients with disease in response, accrual to the trial will be closed with the conclusion that there is little evidence that the response rate would reach 49%. The probability that the trial will close early is 60% if the true response rate is 25%.

If there are ≥ 3 patients with disease in response among 9 evaluable patients, the trial will continue to accrue patients until a total of 20 evaluable patients are entered. If there are ≥ 8 patients w i t h d i s e a s e i n r es p o n s e a m o n g 2 0 evaluable patients, further testing of this regimen will be considered. The probability of concluding the regimen as effective is 81% if the true response rate is 49%. The probability of concluding the regimen as effective is 9% if the true r e s p o n s e r a t e i s 2 5%. Allowing 2 patients to not begin protocol treatment or be classified as ineligible, a total of 22 patients could be entered.

The primary efficacy population includes all eligible patients who begin protocol treatment. The proportion progression-free at 10 months for patients with MTC and the response rate for patients with DTC will be summarized as a proportion with a corresponding exact 95% binomial confidence interval. Safety will be assessed via the CTCAE and frequencies of adverse events will be summarized. Time-to-event endpoints will be estimated using the Kaplan-Meier method and 95% confidence intervals for the median or time-specific event time will be summarized. Another endpoint is to assess quality of life (QOL). QOL will be assessed via self-report questionnaires at the timepoints outlined in the Study Calendar. Descriptive statistics from the responses from the questionnaires will be summarized across timepoints of assessment. Rates of drop-out/non-response to QOL assessments and corresponding reason will also be summarized across timepoints of assessment.

With an estimated monthly accrual of 1 - 2 patients with DTC, the first stage is estimated to complete accrual in approximately 6-8 months. As is customary with this type of design, accrual will be suspended after the first stage (n=9 evaluable patients) in order to assess outcome, however, this suspension is also dependent on the actual observed accrual rate and the number of patients' disease confirmed in CR or PR while the first stage of the trial is accruing.

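### Does the planned exact 95% interval for the DTC response rate need a two-stage p-value and lower bound beside it?

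*Combined protocol and SAP*

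**What the plan says.** All of this is in section 13.1 (Study Design/Endpoints), in the paragraphs on the DTC cohort.

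- **Aim.** The DTC design was "chosen to rule out a best overall response rate of 25" per cent.
- **Stage 1.** Nine evaluable patients; the trial closes with 2 or fewer responders. "The probability that the trial will close early is 60% if the true response rate is 25" per cent.
- **Stage 2.** With 3 or more responders, accrual goes on to 20 evaluable patients. With 8 or more responders of 20, "further testing of this regimen will be considered". "The probability of concluding the regimen as effective is 81% if the true response rate is 49" per cent, and the corresponding probability at a true 25% is given as 9%.
- **Analysis set.** "The primary efficacy population includes all eligible patients who begin protocol treatment".
- **Summary.** "the response rate for patients with DTC will be summarized as a proportion with a corresponding exact 95% binomial confidence interval".
- **Stage sizes.** Up to 22 patients may be entered so as to reach 20 evaluable. Accrual is to be suspended after stage 1, but "this suspension is also dependent on the actual observed accrual rate" and on the responses confirmed while stage 1 is accruing.

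The section plans no p-value, no one-sided bound and no interval that allows for the two stages. It states no nominal significance level and gives the interval no part in the decision.

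**The concern.** The rule and the summary seem to speak different languages. The rule rests on two-stage sampling and accepts about 9% one-sided error. The interval, read in the usual way, treats the 20 patients as one sample and allows about 2.5% error on each side.

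Two things follow. First, at 8 or 9 responders the report would call the regimen worth further testing beside an interval that includes 25%. Second, at exactly 8/20 a reader who checks the result with one-stage binomial methods gets a p-value of 0.102 and a one-sided 90% lower bound of 24.9%, which seem to contradict both the success rule and the stated 9%. Two-stage calculations give 0.090 and 25.6% and agree with the rule.

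If the plan were deficient here, a borderline positive trial could be misread, or the interval could have the wrong coverage because stage 1 was ignored. Borderline results are not rare: 8 or 9 responders make up about a third of all successes when the true rate is 49%.

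**Working it through.** **Inputs, all from section 13.1:** null rate 0.25, alternative 0.49, n1 = 9, continue at 3 or more, n = 20 (11 in stage 2), success at 8 or more.

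**1. The plan's own figures.**

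P(success | p) = sum over x = 3 to 9 of P[Bin(9, p) = x] × P[Bin(11, p) ≥ 8 − x].

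- At p = 0.25 the terms for x = 3 to 8 are 0.02678 + 0.03349 + 0.02121 + 0.00695 + 0.00118 + 0.00010, and the term for x = 9 is negligible. The sum is 0.0897 (stated 9%).
- At p = 0.49 the sum is 0.8062 (stated 81%).
- Early stopping at 0.25 is P[Bin(9, 0.25) ≤ 2] = 0.0751 + 0.2253 + 0.3003 = 0.6007 (stated 60%). At 0.49 it is 0.1001.

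The design is stated correctly.

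**2. One-stage and two-stage values near the threshold.** The two-stage p-value for k responders is P(continue and total ≥ k | 0.25). The two-stage lower bound is the p that solves P(continue and total ≥ k | p) = the chosen tail area. The 95% intervals are Clopper-Pearson.

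| Responders of 20 | Rule | One-stage p | Two-stage p | One-sided 90% bound, one-stage | One-sided 90% bound, two-stage | Ordinary 95% CI | Two-stage 97.5% lower limit |
|---|---|---|---|---|---|---|---|
| 7 | fail | 0.214 | 0.171 | 20.7% | 21.9% | 15.4–59.2% | 16.2% |
| 8 | success | 0.102 | 0.090 | 24.9% | 25.6% | 19.1–63.9% | 19.6% |
| 9 | success | 0.041 | 0.038 | 29.3% | 29.6% | 23.1–68.5% | 23.3% |
| 10 | success | 0.014 | 0.013 | 33.8% | 34.0% | 27.2–72.8% | 27.3% |

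Three readings of the table:

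- The two-stage p-value at 8/20 is 0.0897. It is the same sum as in step 1, so it is the 9% that the plan already prints.
- The one-stage and two-stage methods part company only at 8/20, and by 0.7 percentage points in the bound (25.6 − 24.9).
- At the 95% level, allowing for two stages moves the lower limit from 19.1% to 19.6% at 8/20 and from 23.1% to 23.3% at 9/20. Both still lie below 25%, so the overlap is caused by the confidence level and not by neglect of stage 1.

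**3. Does the ordinary interval cover properly under two-stage sampling?** Summing the exact probability of every final outcome whose interval contains the true rate gives coverage of 98.7% at 25% and 95.9% at 49%. Over true rates from 1% to 99% the minimum is 94.5%, near 60%, and coverage is below 95% only between about 60% and 62%. After a stage-1 stop the ordinary and stagewise limits coincide.

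**4. How often the borderline counts arise.**

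- At 49%: P(8) = 0.1093 and P(9) = 0.1528, together 0.2621, or 0.2621/0.8062 = 32.5% of successes.
- At 25%: P(8) = 0.0513 and P(9) = 0.0249, together 0.0762, or 0.0762/0.0897 = 85.0% of false-positive successes.
- The only count where the two methods read differently, exactly 8, has probability 10.9% at 49% and 5.1% at 25%.

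**5. Would the extra figures always match a result of 8 responders?** The stage sizes below are illustrative assumptions, since the plan allows 22 entered and makes the stage-1 suspension depend on accrual.

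| Stage 1 / total | 8 responders: two-stage p | One-sided 90% bound |
|---|---|---|
| 9 / 20 | 0.090 | 25.6% |
| 10 / 20 | 0.096 | 25.2% |
| 11 / 20 | 0.099 | 25.1% |
| 9 / 21 | 0.110 | 24.5% |
| 9 / 22 | 0.132 | 23.5% |

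With stage 1 closing at 10 or 11, the two-stage p-value also exceeds 9%. With totals of 21 or 22, the two-stage bound no longer excludes 25%.

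**The case for a change.** The best case for a change is that the design exists to rule out 25%, yet the only planned inferential figure fails to do so at two of the qualifying counts, and the plan does not explain this. Those counts are central for a 20-patient cohort. The two-stage p-value and one-sided 90% lower bound agree with the rule at 7, 8 and 9 responders when the stage sizes are 9 and 20. They would take two or three sentences to specify, and fixing them in advance would avoid a later choice of method.

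The arithmetic stands, and a sentence noting that the 95% interval may include 25% at 8 or 9 responders would help a reader. The rest does not amount to a defect. The conflict at 8/20 is with a one-stage p-value and a 90% bound that the plan never proposes, at a level it never states. Agreement also depends on that level: the two-stage one-sided lower bound at 8/20 is 25.6% at 90% confidence, but 22.3% at 95% and 19.6% at 97.5%. As step 5 shows, it depends on the exact stage sizes too, whereas the ordinary interval can be computed for whatever number of patients is reached.

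**Conclusion.** The concern does not hold. A report that follows section 13.1 exactly applies a correctly calibrated count rule (0.0897 error at 25%, 0.8062 power at 49%) and gives a descriptive interval whose coverage under the two-stage design never falls below 94.5%. A 95% interval that includes 25% at 8 or 9 responders does not contradict a rule with about 9% one-sided error; it is a stricter statement about the same data, and a two-stage interval at that level includes 25% as well. The design-based p-value at the threshold is the 9% in the text.

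The one real difference between methods is confined to exactly 8/20 (10.9% of trials at a true 49%, 5.1% at 25%) and changes no decision. The stated consequence of success is also modest: further testing is to be considered. Extra two-stage output is a matter of reporting taste.

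This rests on reading the planned interval as Clopper-Pearson, on stage sizes of 9 and 20 for the main figures, and on the one-sided 90% level, which is an assumption because the documents give no nominal level. At the stated 9% the reading is the same: two-stage 0.0897 lies just below it, one-stage 0.1018 above.

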14. PUBLICATION PLAN

The results should be made public within 24 months of reaching the end of the study. The end of the study is the time point at which the last data items are to be reported, or after the outcome data are sufficiently mature for analysis, as defined in the section on Sample Size, Accrual Rate and Study Duration. If a report is planned to be published in a peer-reviewed journal, then that initial release may be an abstract that meets the requirements of the International Committee of Medical Journal Editors. A full report of the outcomes should be made public no later than three (3) years after the end of the study.

APPENDIX A PERFORMANCE STATUS CRITERIA

ECOG Performance Status Scale			Karnofsky Performance Scale			
Grade	Descriptions	Percent	Description			
0	Normal activity. Fully active, able to		Normal, no complaints, no evidence of disease.			
	carry on all pre-disease performance without restriction.	90	Able to carry on normal activity; minor signs or symptoms of disease.			
1	Symptoms, but ambulatory Restricted in physically strenuous activity, but ambulatory and able to	80	Normal activity with effort; some signs or symptoms of disease.			
	carry out work of a light or sedentary nature (e.g. , light housework, office work).		Cares for self, unable to carry on normal activity or to do active work.			
	In bed <50% of the time Ambulatory and capable of all self-	60	Requires occasional assistance, but is able to care for most of his/her needs.			
2	care, but unable to carry out any work activities. Up and about more than 50% of waking hours.	50	Requires considerable assistance and frequent medical care.			
3	In bed >50% of the time. Capable of	1	Disabled, requires special care and assistance.			
	bed or chair more than 50% of waking hours.		Severely disabled, hospitalization indicated. Death not imminent.			
4	100% bedridden. Completely disabled. Cannot carry on any self-		Very sick, hospitalization indicated. Death not imminent.			
	care. Totally confined to bed on chair.	10	Moribund, fatal processes progressing rapidly.			
5	Dead.	0	Dead.
